Subjects will receive a consent form at least 24 hours in advance of the study session. This will allow subjects sufficient time to read over the form on their own, and come up with any questions or concerns prior to the commencement of the session. Before the session begins, study personnel will review the consent form and experimental procedure with the subject and answer any questions. The subject will then be given the opportunity to sign the consent form, with study personnel witnessing. Any subjects that decline to sign the consent form will be dismissed at that time. In addition to the written informed consent that patients will sign prior to commencing their first session in the Rehabilitation Robotics Lab, an oral informed consent will be read to all prospective participants over the phone. When a subject is either contacted by a member of the research team or calls our lab inquiring about the study, the oral consent will be read prior to asking questions from the phone screening form or the Beck Depression Inventory.

Children and Adolescents

Not applicable.

Adult Subjects Not Competent to Give Consent

Yes. In fact, one of the exclusion criteria for this study is cognitive impairment. Thus, all subjects will be competent. See section on exclusion criteria for more details.

2. Waiver of Consent

Waiver or Alteration of Informed Consent*

No Waiver Requested

Minimal Risk*

Impact on Subject Rights and Welfare*

Waiver Essential to Research*

Additional Information to Subjects

Written Statement of Research*

No

If no written statement will be provided, please provide justification

The following documents are currently attached to this item:

There are no documents attached for this item.

Risk / Benefit

Potential Study Risks

Subjects may experience fatigue or muscle strain if exercises are too intense. In the event of a robot malfunction, subjects may experience muscle strain or minor bruises. To minimize risk of injuries due to exercise, the intensity will be kept in the mild to moderate range. Exercise intensity must also be kept low in order to reduce the confounding effect of fatigue on experimental results. After each exercise, subjects will be questioned regarding the difficulty of the task, exercise intensity, and their discomfort level. At that time, the protocol will be adjusted accordingly. Subjects will be given ample time to rest as part of the experiment protocol. Risk of injury from the robot stems from its ability to exert large forces. Therefore, we have implemented several layers of protection to prevent the robot from exerting forces that might cause injury. For example, the software permits the robot's commanded force to be limited and a stop command to be issued to the robot. In addition, the current to the motor that determines the forces is limited by a current limiter that will maintain current to a preset level. As a backup, there is a limit switch that will cut power to the motor if excessive forces are detected. And as a final level of backup, another mechanical method (torque limiter) has been put in place that limits forces and is capable of physically disengaging the motor from the handle that the patient is gripping. A spring inside the robot allows it to be compliant, which reduces the ability of patients to feel sudden starts or stops of the motor, and reduces the risk of injury in the event of a robot-patient collision. Padding on the robot provides further protection against any impacts. Furthermore, an emergency stop switch will be made available to both the subject and operator; it will cut power to the motor when triggered. If a subject is experiencing a level of pain great than three (mild) on the Visual Analog Pain Scale, the session will be stopped.

Potential Study Benefits

There are no direct, major benefits to a particular subject. Participation will help advance rehabilitation robotics research.

Alternatives to Participation (optional)

Data and Safety Monitoring

The principal investigator will monitor this protocol. See attached for the D&SM Plan.

The following documents are currently attached to this item:

There are no documents attached for this item.

Risk / Benefit Assessment

The risks involved in A and B are minimal - fatigue, frustration, minor bruising. There are no immediate direct benefits to study participants. Possible benefits to society are significant, as according to the American Heart Association, every year, 15 million people suffer a stroke. Most people survive the stroke, but have subsequent problems and many require assistance for activities of daily living.

General Attachments

The following documents are currently attached to this item:

Additional forms ([name]-citicompletionreport.pdf)

Additional forms ([name]-citicertificate.pdf)

Additional forms ([name]-citirefresher-2018.08.29.pdf)

Additional forms ([name]-citirefresher2018.08.08.pdf)

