TheraDrive is a low-cost robotic system for post-stroke upper extremity rehabilitation. The system uses off-the-shelf computer gaming wheels with force feedback to help reduce motor impairment and improve function in the arms of stroke survivors. Preliminary results from various studies have shown that the original TheraDrive system lacked a robust mechanical linkage which could withstand the forces exerted by patients, lacked a patient-specific adaptive controller to deliver personalized therapy, and was not capable of delivering effective therapy to severely low-functioning patients. A new low-cost, high-force haptic robot with a single degree of freedom has been developed to address these concerns. This study has two purposes: first, to test the viability and usability of the new robot system alongside the original TheraDrive system; and second, to test if low-functioning patients benefit, and if so how much, from using force-feedback therapy as opposed to devices with zero impedance. This will be done by recruiting approximately 36 human subjects. Exercises will be performed by study subjects and an adaptive controller will monitor patient performance to ensure that exercises are difficult but doable, which is important for maintaining patient motivation. We hypothesize that not only will the new system be viable, but that it will provide better robot-assisted therapy to a large variety of patients, especially low-functioning stroke survivors with hemiplegia.

Objectives

Overall objectives

This study is being performed to assess the usability of affordable force-feedback devices for stroke rehabilitation. For this pilot study, subjects will use two or more devices (a commercial force-feedback

joystick, commercial force-feedback wheel, and a custom force-feedback device) to complete games and exercise tasks to determine the ease of using these devices and their impact on motor performance and function. The long-term goal of this project is to develop an inexpensive high-force haptic rehabilitation robot that can safely be used by patients at home without therapist supervision. A sub-goal was to simulate the human-machine interaction. We will use our assessment tools to determine upper arm kinematic and dynamic workspace recovery

Primary outcome variable(s)

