Part A Usability Study: Cross-sectional study comparing outcome variables for stroke survivors with varying levels of motor deficit impairment in their upper extremity. Subjects with mild motor deficits will be compared against stroke survivors with severe motor deficits after completing exercises with both commercial and custom therapy devices. Therapy exercises will be performed in random order, decided prior to the session. It will be randomly determined which robot the patient will use first, the order of operating modes used for the new robot, and the order of therapy exercises performed in each mode. Surface Electromyography (EMG) will be used in order to detect the small electric currents, or signals, which are generated by muscle activity. The collection of the strength and pattern of the signals will permit us to verify muscle activity over time. Part B Therapy Study: Pre-post study looking at change in outcome variables over 12 therapy sessions (three times a week for one month). Only low and mid functioning stroke survivors will be asked to participate in Part B of the study, and only the custom haptic device will be used by the study subjects. Pre-post evaluations will be administered at session 1 and 12. Surface Electromyography (EMG) will be used in order to detect the small electric currents, or

signals, which are generated by muscle activity. The collection of the strength and pattern of the signals will permit us to verify muscle activity over time.

Study duration

1) We estimate that it will take 3 years from the date of IRB approval to enroll all subjects and complete the study. 2) Part A - The subject's participation in the study will be limited to approximately 4 hours; 1-2 hours to be evaluated by a therapist with expertise in stroke rehabilitation and 2-3 hours of assessing the viability and usability of the various therapy devices. Part B - Subjects enrolled in Part B will be asked to return 3 times a week for 1 month (12 sessions). All sessions will last approximately 1.5 hours. 3) Projected date of the proposed study: 3/1/14 to 7/1/17.

Resources necessary for human research protection

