
The following documents are currently attached to this item:

There are no documents attached for this item.

Deception

Does your project use deception?

No

Analysis Plan

1) Clinical data will be analyzed to determine how subjects low versus high function perform on metrics developed using the robots. 2) Trajectory tracking using a baseline with zero resistance will be established for each patient. The root mean square metric will be used to assess accuracy in tracking tasks and subjects' performance across groups (low versus high) and devices in Part A, and across time in Part B. Using a 2-way ANOVA test for Part A, and an alpha of 0.05, significant difference across groups will be detected. A paired t-test, and an alpha of 0.05, will detect significant difference across time pre-post the 12 sessions. 3) Data collected from the surface EMG will be analyzed to verify muscle activity over time. 4) Data results will be used to build a simulation model of the human-robot tracking and determine a prediction of the joint and muscle forces that are used in Part A and Part B. 5) Data collected with the kinect will be assessed for kinematic and dynamic workspace. The data will be fitted to a computerized model of the upper limb to extract forces and positions defining dynamic and kinematic workspace.

The following documents are currently attached to this item:

There are no documents attached for this item.

Are you conducting research outside of the United States?

No

Data confidentiality

x Paper-based records will be kept in a secure location and only be accessible to personnel involved in the study.

x Computer-based files will only be made available to personnel involved in the study through the use of access privileges and passwords.

Prior to access to any study-related information, personnel will be required to sign statements agreeing to protect the security and confidentiality of identifiable information.

x Wherever feasible, identifiers will be removed from study-related information.

A Certificate of Confidentiality will be obtained, because the research could place the subject at risk of criminal or civil liability or cause damage to the subject's financial standing, employability, or liability.

A waiver of documentation of consent is being requested, because the only link between the subject and the study would be the consent document and the primary risk is a breach of confidentiality. (This is not an option for FDA-regulated research.)

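### The second purpose, benefit of force feedback over zero impedance in low-functioning patients, is matched by no planned test

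*Combined protocol and SAP*

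**What the plan says.** The Abstract gives two purposes. The first concerns viability and usability of the new robot. The second is "to test if low-functioning patients benefit, and if so how much, from using force-feedback therapy as opposed to devices with zero impedance".

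The Overall objectives list three devices: a joystick, also described there as commercial force-feedback, and a "commercial force-feedback wheel, and a custom force-feedback device".

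Under Design, Part A is cross-sectional and compares stroke survivors with mild and severe motor deficits. On order it says: "It will be randomly determined which robot the patient will use first, the order of operating modes used for the new robot". The modes are not defined. Part B is a pre-post study over 12 sessions, in which "only the custom haptic device will be used by the study subjects".

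Item 2 of the Analysis Plan contains the tests:
- A reference condition is named: "Trajectory tracking using a baseline with zero resistance will be established for each patient".
- The Part A test is worded in this way: "Using a 2-way ANOVA test for Part A, and an alpha of 0.05, significant difference across groups will be detected".
- The factors for the root mean square (RMS) tracking metric are given as "performance across groups (low versus high) and devices in Part A, and across time in Part B".
- The Part B test is worded in this way: "A paired t-test, and an alpha of 0.05, will detect significant difference across time pre-post the 12 sessions".

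Under Procedures, Part A, each robot is moved with the handle unloaded and then with pressure on it, always in that order.

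**The concern.** The second purpose is comparative and quantitative. A reader would expect at least one analysis that sets force-feedback therapy against zero impedance in low-functioning patients and reports the size of the difference. None is named.

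Two things are at stake. First, a significant pre-post change in Part B may later be taken as the answer to whether patients benefit and by how much, although it carries no information about zero impedance. Second, the plan may already produce zero-resistance tracking data that could support a limited comparison. With no test specified, those data may go unanalysed, or be analysed in a way chosen after the results are seen.

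**Working it through.** The plan gives no power, effect size or standard deviation, and justifies its sample size only by pilot status. There is no figure to reproduce, so the check sets the purpose against each planned test.

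**1. The quantity promised.** In low-functioning patients, let D_F be the mean change over a course of force-feedback therapy and D_Z the mean change over a course at zero impedance. The purpose asks for θ = D_F − D_Z.

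**2. Part B.** There is one group on one device, and the number of zero-impedance courses is 0. The paired t-test addresses the null hypothesis D_F = 0. Since D_F = θ + D_Z, the result determines θ only if D_Z is known, and nothing in the documents supplies it. Suppose zero-impedance training produced exactly the same gain, so that D_Z = D_F and θ = 0. The t-test would still reject with its full power against D_F. More subjects narrow the interval for D_F and leave θ undetermined.

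**3. Part A ANOVA.** The factors described are group and device.
- The group effect compares low with high function.
- The device effect compares members of a list of 3 devices, of which 3 are called force-feedback and 0 zero-impedance.
- A group-by-device interaction would ask whether device differences vary with function.

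None of these contrasts force feedback with its absence.

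**4. The zero-resistance baseline.** A usable contrast needs four facts about it.

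| Needed | Stated? |
|---|---|
| Part in which it is recorded | No; the sentence precedes the split between Parts A and B |
| Device | No |
| Place in the order of runs | No |
| Test against a force-feedback run | No |

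The operating modes in the Design section might include a zero-impedance mode, but they are undefined. The unloaded and loaded handle sequence in Procedures is not described as a change in robot impedance. If it is the source of the baseline, its fixed order would confound condition with practice and fatigue.

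**5. What a Part A contrast could show.** Part A is cross-sectional. A difference in tracking RMS between two conditions there describes performance at the time of testing. It is not a change over a course of therapy in Fugl-Meyer, ADL function or grip strength, so it is not θ.

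**6. What Part B can support.** It can estimate D_F, but two inputs are unsettled.
- The Design section places evaluations at sessions 1 and 12. Procedures says that subjects coming from Part A are not re-evaluated by a therapist. Accrual hopes that all low-functioning Part A subjects will continue, so for many the clinical pre-value may date from Part A.
- The Design section admits low and mid functioning survivors to Part B. Key inclusion criteria and Procedures admit low functioning only.

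**The case against.** The strongest reply is that zero resistance is not absent from the plan. A zero-resistance baseline is promised for every patient, and operating-mode order on the new robot is randomised, so a within-subject comparison may be possible. That stands. A reader might infer that the study collects nothing at zero resistance, and the documents do not support so strong a reading. Nor do they support the opposite one, that Part A certainly holds the needed data, because the baseline is not tied to a Part or a device.

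A second reply is that this is a pilot, that the Overall objectives omit the zero-impedance contrast, and that the t-test is described only as a test across time. This also stands in part. A reader might infer that the plan claims Part B will prove superiority to zero impedance, but it makes no such claim for that test. Misreading is a risk, not a stated intention. Pilot status excuses low power, however; it does not supply a missing comparator for a purpose that the Abstract states.

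Third, a comparator might come from elsewhere. Subject compensation mentions a Part C, and Subject recruitment allows data from protocol #823511 to be included. Part C is described nowhere, and the other protocol is mentioned only for its similar recruitment population. Neither is stated to provide a zero-impedance course.

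**Conclusion.** The point holds: no planned test contrasts force feedback with zero impedance, in low-functioning patients or otherwise. For Part B the gap is structural. With no zero-impedance course, benefit over zero impedance is not estimable at any sample size. For Part A the finding is narrower: a comparison may be possible, but none is specified, and it could speak only to immediate performance.

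This rests on two assumptions. The current text is taken to describe all planned therapy and tests. Zero impedance (Abstract, said of devices) and zero resistance (Analysis Plan, said of a baseline) are taken as close enough for an exploratory contrast, although neither is defined. Comparing two conditions on one robot remains a narrower question than the device comparison in the Abstract. The matter affects what the study can conclude, not safety, and should be corrected.

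**What to change.** 1. **Abstract.** Restate the second purpose in two parts.
   - (a) Exploratory: where a zero-resistance run and a force-feedback run on the custom robot exist for the same subject, estimate the immediate difference in tracking RMS in low-functioning subjects.
   - (b) In Part B, estimate within-subject change from the pre-assessment to the post-assessment after session 12 in tracking RMS, upper extremity Fugl-Meyer, ADL function and grip strength, with no claim of benefit over zero impedance.

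   Name these outcomes one by one. A general reference to the primary outcomes would take in the MRI measures listed there, although the application answers No on research MRI.

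2. **Analysis Plan.** Add a within-subject comparison of zero-resistance with force-feedback tracking RMS, including a group (low versus high) by condition interaction. Report the effect in low-functioning subjects with a 95% CI, as immediate performance. State the Part, device and operating mode of each run. If the order was fixed, report the contrast as confounded with order. If no zero-resistance run on the custom robot exists, state that (a) cannot be answered. Date the change, and label it post hoc if data have already been examined.

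3. **Reconcile.** Bring the session 1 evaluation in Design into line with the no-re-evaluation rule in Procedures, so that the pre-value in (b) is defined. Reconcile the Part B population across Design, Key inclusion criteria and Procedures.

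The cost is wording and one exploratory analysis. No subjects or visits are added: if the runs were not recorded, (a) is declared unanswerable. The downside is a more modest claim, with the comparative therapy question left to a later controlled study.

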If the change represents more than minimal risk to subjects, it must be reviewed and approved by the IRB at a convened meeting. For a modification to be considered more than minimal risk, the proposed change would increase the risk of discomfort or decrease benefit. The IRB must review and approve the proposed change at a convened meeting before the change can be implemented unless the change is necessary to eliminate an immediate hazard to the research participants. In the case of a change implemented to eliminate an immediate hazard to participants, the IRB will review the change to determine that it is consistent with ensuring the participant's continued welfare. Examples: Convened Board Increase in target enrollment for investigator initiated research or potential Phase I research Expanding inclusion or removing exclusion criteria where the new population may be at increased risk Revised risk information with active participants Minor risk revisions that may affect a subject's willingness to continue to participate Expedited Review Increase in target enrollment at Penn where overall enrollment target is not exceeded or potentially sponsored research Expanding inclusion or removing exclusion where the new population has the same expected risk as the previous, based on similarities of condition Revised risk information with subjects in long-term follow-up Minor risk revisions with no subjects enrolled to date Expedited Review

Modification Summary

Please describe any required modification to the protocol. If you are using this form to submit an exception or report a deviation, enter 'N/A' in the box below.

Adding [name] as study contact, updating [name], [name] and [name] human cert, and removing [name], who is no longer involved in the study. The protocol will also be changed to allow for the inclusion of data only, from protocol 823511, which has similar recruitment population.

Risk / Benefit

Does this amendment alter the Risk/Benefit profile of the study?

No

Change in Consent

Has there been a change in the consent documents?

No

If YES, please choose from the options below regarding re-consenting

Deviations

Are you reporting a deviation to this protocol?*

No

Exceptions

Are you reporting an exception to this protocol?*

No

Protocol Details

Resubmission*

Yes

Study Personnel

Principal Investigator

Name:	[name]
Dept / School / Div:	4482 - RM-Rehabilitation Medicine
Campus Address	4283

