Research Device Management*

Please indicate how research device(s) will be managed.

The device receipt, storage and dispensing is being conducted by the research team (please provide information in the protocol summary as to how this will be conducted)

Drug, Herbal Product or Other Chemical Element Management *

Please indicate how drugs, herbal products or other chemical entities will be managed.

Not Applicable (no drugs, herbal products or other chemical entities)

Radiation Exposure*

Are research subjects receiving any radiation exposure (e.g. X-rays, CT, Fluoroscopy, DEXA, pQCT, FDG, Tc-99m, etc.) that they would not receive if they were not enrolled in this protocol?

No

Gene Transfer*

Does this research involve gene transfer (including all vectors) to human subjects?

No

Human Source Material*

Does this research include collection or use of human source material (i.e., human blood, blood products, tissues or body fluids)?

No

CACTIS and CT Studies*

Does the research involve Center for Advanced Computed Tomography Imaging Services (CACTIS) and CT studies that research subjects would not receive if they were not part of this protocol?

No

CAMRIS and MRI Studies*

Does the research involve Center for Advanced Magnetic Resonance Imaging and Spectroscopy (CAMRIS) and MRI studies that research subjects would not receive if they were not part of this protocol?

No

Investigational Agent or Device within the Operating Room*

Does the research project involve the use of an investigational agent or device within the Operating Room?

No

Cancer Related research not being conducted by an NCI cooperative group*

Does this protocol involve cancer-related studies in any of the following categories?

No

Processing of Materials*

Will the research involve processing (such as over encapsulating, or compounding)?

No

In-House Manufacturing of Materials*

Will the research involve processing (such as over encapsulating, or compounding)?

No

Medical Information Disclosure*

Does the research proposal involve the use and disclosure of research subject's medical information for research purposes?

No

If the answer is YES, indicate which items is is provided with this submission:

CTRC Resources*

Does the research involve CTRC resources?

No

Pathology and Laboratory Medicine Resources*

Will samples be collected by hospital phlebotomy and/or processed or analyzed by any of the clinical laboratories of the University of Pennsylvania Health System?

No

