The primary outcomes are motor control, as measured by the upper extremity Fugl-Meyer; ADL function; and grip strength as measured by a dynamometer; a custom metric to determine Kinematic workspace and dynamic workspace will be employed. Customized metrics will be defined such as movement time, movement velocity, and accuracy. New outcome variables related to MRI: fiber density and hemisphere activation

Secondary outcome variable(s)

The secondary variables for motor impairment are upper extremity coordination, finger dexterity, and spasticity - the Box and Block and Ashworth assessments will be used to evaluate these.

Background

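### Two MRI measures under the primary outcome heading have no stated source, timing or analysis, and the one tested metric, RMS tracking accuracy, is not designated primary in either part.

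*Combined protocol and SAP*

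**What the plan says.** **Outcomes.** The section on primary outcome variables opens: "The primary outcomes are motor control, as measured by the upper extremity Fugl-Meyer; ADL function; and grip strength as measured by a dynamometer". The same section adds a custom metric for kinematic and dynamic workspace, then "Customized metrics will be defined such as movement time, movement velocity, and accuracy", and ends with "New outcome variables related to MRI: fiber density and hemisphere activation". None of these is ranked or assigned to Part A or Part B.

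**MRI elsewhere.** The only other mention is the CAMRIS and MRI item, which asks about "MRI studies that research subjects would not receive if they were not part of this protocol" and is answered no. The form also answers no under Medical Information Disclosure, and no under Use of UPHS services, an item that covers routine care as well as research. The Modification Summary says that the protocol will "allow for the inclusion of data only, from protocol 823511, which has similar recruitment population", and Subject recruitment carries the same provision. Subject compensation mentions a Part C that is described nowhere else.

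**Design.** Overall objectives states: "For this pilot study, subjects will use two or more devices". The Design section describes Part B as a "Pre-post study looking at change in outcome variables over 12 therapy sessions" and adds: "Pre-post evaluations will be administered at session 1 and 12".

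**Tests.** Item 2 of the Analysis Plan uses RMS to assess tracking accuracy, across groups and devices in Part A and across time in Part B. It then names a two-way ANOVA for Part A, to detect differences across groups, and a paired t-test for Part B, each at alpha 0.05. No other item carries a test or an alpha.

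**The concern.** Two problems meet here. First, two measures sit under the primary heading with no route to being collected, so a reader cannot tell whether they will exist, for whom, or at what time. Second, the outcomes called primary and the outcome that is tested are different things. Fugl-Meyer, ADL function and grip strength have no assigned test. RMS tracking accuracy has a test, but among the primary outcomes accuracy appears only as an example in an open list.

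Two analysts could follow this plan faithfully and report different primary results, so the choice could be made after the data are seen. A pilot may carry many outcomes. This one, however, plans significance tests and sets out in its Abstract to test whether low-functioning patients benefit and by how much, so it should say in advance which comparison answers that question.

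**Working it through.** The plan gives no power, effect size or standard deviation, so there is no figure to reproduce. The check sets the sections side by side, followed by two short calculations.

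**1. Can the MRI measures arise from the plan as written?**
- Design: EMG and pre-post evaluations; no scan.
- Procedures, Parts A and B: clinical assessments, Kinect workspace assessment, EMG and device work; no scan. The assessment lists end in an open *etc.*, which cannot be relied on to imply MRI.
- Analysis Plan: items on clinical data, RMS, EMG, simulation and Kinect; none on MRI. EMG and Kinect each have both a procedure and an analysis item, whereas MRI has neither.
- Possible sources: data from protocol 823511, Part C, or existing scans. No section links any of them to MRI. Existing clinical scans may also conflict with the two no answers on medical information and UPHS services.

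**2. Which outcome has a test?**

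| Outcome | Called primary, or under the heading | Test assigned |
|---|---|---|
| Fugl-Meyer, ADL function, grip strength | Called primary | None specifically |
| Kinematic and dynamic workspace | Under the heading | None |
| Movement time, movement velocity | Under the heading, as examples | None |
| Accuracy (RMS) | Under the heading, as an example | ANOVA (Part A); paired t-test (Part B), on the plain reading |
| Fiber density, hemisphere activation | Under the heading | None |

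The t-test sentence names no endpoint. Its position in the RMS item points to RMS, but the Design section speaks of change in outcome variables generally.

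**3. False positives from the number of outcomes (illustration only).** With k independent tests at 0.05 and any one success counting, the rate is 1 − 0.95^k.
- k = 3: 1 − 0.95³ = 0.143.
- k = 8 (all named variables without MRI): 1 − 0.95⁸ = 0.337.
- k = 10 (with MRI): 1 − 0.95¹⁰ = 0.401.
- At an assumed equal correlation of 0.5, the rates are 0.125, 0.250 and 0.287.
- One valid RMS test per part: 0.05 per part.

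The count of 10 takes workspace as two measures and the open list as three. The plan states neither one test per outcome nor an any-success rule.

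**4. The Part A ANOVA.** Each subject contributes a value for each of m devices. Let ρ be the correlation between values from one subject (assumed; not in the plan). An ordinary two-way ANOVA treats all values as independent.
- Group effect: the true variance is 1 + (m − 1)ρ times the assumed variance. In the normal approximation the actual type I error is 2 × P(Z > 1.96/√(1 + (m − 1)ρ)).
- m = 2, ρ = 0.5: 1.96/√1.5 = 1.600, giving 0.110.
- m = 3, ρ = 0.5: 1.96/√2 = 1.386, giving 0.166.
- Range for ρ from 0.3 to 0.7: 0.086 to 0.133 for two devices; 0.121 to 0.206 for three.
- Simulation with 36 subjects (the Abstract's approximate figure) and ρ = 0.5: about 11% and 17%, in agreement.
- Device effect: the true variance is 1 − ρ times the assumed variance. At ρ = 0.5, 1.96/√0.5 = 2.77, giving about 0.006 for a two-device contrast. The device comparison therefore becomes far too conservative.

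**The case against.** The strongest reply is that the tests are not ambiguous. The plan names one test per part at a stated alpha, in an item whose only metric is RMS, so the plain reading is RMS for both. That stands. A reader might infer from the missing primary designation that no test is named at all, and the Analysis Plan does not support that. What remains is that RMS is not designated primary, while the outcomes called primary have no assigned test.

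A reader might also infer a false-positive rate of up to 40%. That needs a test on every listed variable and a rule that any success counts, and the plan contains neither. Nor is 10 a firm count: the list is open, and workspace is described as a single custom metric. These figures illustrate what an undesignated list could allow and do not measure the plan's error rate.

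A third tempting inference is that the MRI measures are ruled out by the form's own answer. The question covers only scans that subjects would not otherwise receive, so imported data or existing scans remain possible. The source is unstated; it has not been shown to be impossible.

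Finally, this is a pilot with no stated confirmatory claim. Formal multiplicity adjustment of every remaining outcome would be a preference, and it is not asked for here. The pilot label does not, however, supply a source for MRI or say which result is primary.

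**Conclusion.** The point holds in this form, from the text alone. Two measures under the primary heading have no stated source, timing or analysis. The three outcomes explicitly called primary have no assigned test, and the one metric tied to the tests is not designated primary in either part.

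With only RMS tested, by one valid test per part, the error rate is 5% per part. That assumes a single named effect, since a two-way ANOVA can yield two main effects and an interaction. It also assumes an analysis that respects repeated use of devices. If the ANOVA is run as an ordinary one, the group test would run at about 11% (two devices) or 17% (three) under the assumed correlation of 0.5. The plan does not say whether a repeated-measures form is intended.

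The sections disagree on the Part B clinical baseline: Design places evaluations at sessions 1 and 12, while Procedures says that subjects from Part A are not re-evaluated by a therapist. That is a separate matter, and it bears on this point only if Fugl-Meyer becomes the Part B primary outcome.

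**What to change.** 1. **MRI.** Move fiber density and hemisphere activation to exploratory outcomes and state source, subjects, timing and analysis, or delete them. Reconcile the form's answers on MRI, medical information and UPHS services with whichever source is named.
2. **Primary outcome and test.** Before outcome data are analysed, designate one of each per part.
   - Part A: RMS tracking error, with the primary effect named. Group follows the Analysis Plan; device fits the usability aim in the Abstract better.
   - Part B: one paired pre-post comparison, on either RMS or Fugl-Meyer. If Fugl-Meyer is chosen, Design and Procedures must first be reconciled on when the baseline is taken.
   - Label all other outcomes secondary or exploratory and report them with confidence intervals.
3. **Part A model.** Specify a mixed (repeated-measures) ANOVA with group between subjects and device within subject.
4. **Timing.** If outcome data have already been seen, disclose the choice as post hoc.

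**Cost.** Items 2 to 4 need wording and a small change of analysis. Item 1 is wording if MRI is dropped or imported. Existing clinical scans would also need the form's answers revisited, and scans done under this protocol would need procedure and risk text added and reviewed. The downside is that fewer results can be called primary.
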